Outcomes have been aligned as far as possible with the relevant Brighton/GAIA outcome definitions, and also agreed with those in the MHRA / four nations working group on COVID-19 vaccination in pregnancy and comply with those recommended by the WHO³. See Appendix 2 for full rational and sources of information behind included outcomes, definitions, timings etc. as presented in Table 2.

Both primary and secondary outcomes are of interest, with the former being a composite measure including the associated secondary outcomes, and the latter being a narrower measure or subset of the associated primary outcome, e.g. primary outcome = small for gestational age, secondary outcome = very small for gestational age.

Venous thromboembolism in pregnancy is a standard maternal outcome that may be influenced by infection or vaccination and is not the same as vaccine associated thrombosis with thrombocytopenia (VATT), the condition associated with the AstraZeneca vaccine⁴. Similarly, the pregnancy related bleeding outcome includes disseminated intravascular coagulation (DIC) which can occur in association with massive obstetric haemorrhage: again, this is distinct from VATT. Full lists of ICD10 codes used to identify the maternal outcomes venous thromboembolism, pregnancy-related bleeding, and hypertensive disorders of pregnancy are shown in Appendix 1.

³ <https://www.who.int/publications/m/item/safety-surveillance-of-covid-19-vaccines-in-pregnant-and-breastfeeding-women>

⁴ Pavord, S et al (2021). Clinical Features of Vaccine-Induced Immune Thrombocytopenia and Thrombosis. NEJM. DOI: 10.1056/NEJMoa2109908

'Clean windows' will be applied to outcomes, where appropriate, so that only new or incident cases occurring post vaccination will be counted. Specifically, a clean window of the current pregnancy will be applied for the venous thromboembolism, pregnancy-related bleeding, and hypertensive disorders of pregnancy outcomes (i.e. women will only be included if there is no prior record of these outcomes in the current pregnancy). See Table 2. For both congenital anomalies and pregnancy-related bleeding, further descriptive analyses will be conducted looking at more specific diagnoses within these broader outcome groups if we find evidence for an association between vaccination and these outcomes. For example, for pregnancy-related bleeding, we can further disaggregate into early pregnancy bleeding, obstetric haemorrhage, and DIC.

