Longer term child outcomes, including immune function and infection, and neurodevelopment, will be addressed in future work as required.

Other adverse outcomes that are not specific to pregnant women, will be investigated separately for the whole population as part of wider adverse events monitoring in Scotland. If these analyses suggest any signals in the pregnant population, those outcomes would be investigated in the pregnant population using the COPS data infrastructure, as required.

Table 2: Maternal, pregnancy and neonatal outcome measures for monitoring of safety of COVID-19 vaccination in pregnancy

Outcome measure	Definition	Primary or secondary outcome?	Clean window requirement to identify incident cases	Timing of vaccination to be included	Post vaccination risk period to be examined	Estimated background risk of outcome (%)
Maternal outcomes						
Hypertensive disorders of pregnancy	See ICD10 code list. Note that hypertensive disorders can only be diagnosed at >20 weeks.	Primary	No prior record in this pregnancy	Any	Up to E plus PP	10.0
Venous thromboembolism	See ICD10 code list	Primary	No prior record in this pregnancy	Any	Up to E plus PP	0.15
Pregnancy-related bleeding	See ICD10 code list	Primary	No prior record in this pregnancy	Any	Up to E plus PP	30.0 (for postpartum haemorrhage)
ICU admission or death (any cause)	ICU admission as identified on SICSAG record Death from any cause	Primary	None (but exploration to be undertaken of reasons for any pre-vaccination ICU admission where these are documented)	Any	Up to E plus PP	Unknown
Pregnancy outcomes						
Miscarriage	Miscarriage at <24 completed weeks gestation	Primary	None	Up to 23w+6d gestation	Up to 23+6 gestation	10.0 – 20.0

• First trimester miscarriage	Miscarriage at <14 completed weeks gestation	Secondary	None	Up to 13+6 gestation	Up to 13+6 gestation	Unknown
• Second trimester miscarriage	Miscarriage at 14-<24 completed weeks gestation	Secondary	None	Up to 23+6 gestation	14+0 to 23+6 gestation	Unknown
Ectopic pregnancy	Ectopic pregnancy ending at any gestation	Primary	None	Up to 2+6 gestation	Up to E	1.0
Stillbirth	Spontaneous fetal loss at ≥24 completed weeks gestation Any cause of fetal death Losses related to termination of pregnancy excluded	Primary	None	Any	24+0 to E	0.4
Baby outcomes (live births only unless otherwise stated)						

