Notes: If timing of vaccination during pregnancy is specified as 'any', this means that women vaccinated at any point from six weeks preconception to date of end of pregnancy (E) will potentially be included in the analysis dependent on the woman being followed-up to the end of the outcome-specific follow-up period. For longer term risk periods: E is date of end of pregnancy; PP is mother's postpartum period, i.e. 6 weeks following delivery (E to E+41); NN is baby's neonatal period, i.e. 4 weeks following live birth (E to E+27). The pregnancy specific maternal outcomes listed above require follow-up to the end of the postpartum period (E+41) for mothers and the end of the postnatal period (E+27) for babies.

3.5.2: Exposure

The primary exposure to be investigated in the analyses is **any** receipt of COVID-19 vaccine from six weeks before conception to the end of an outcome-specific exposure period within pregnancy (Yes/No). The exposure periods for vaccination varies for each outcome (referred to as “outcome-specific exposure period” throughout this protocol), as outlined in Table 2. For ectopic pregnancy, for example, the exposed group will include women who were vaccinated between six weeks before conception up to 2⁺⁶ weeks gestation, while for stillbirth the vaccine exposure period is extended up to the end of the pregnancy.

Subgroup analyses will be conducted where sample size permits, further stratifying women who received their COVID-19 vaccine within the outcome-specific exposure period by: (1) the number of doses received; (2) by the class of vaccine(s) received and; (3) by the type of vaccine(s) received. For the latter two subgroup analyses, we will exclude women who received multiple different classes or types of vaccine within the outcome-specific exposure period. These results will need to be interpreted with caution given that some types of vaccination will be linked to specific sub-groups of women. For example, early in the vaccination programme women who were frontline health or care workers were more likely to receive the Pfizer/BioNTech vaccine, whereas women who were clinically (extremely) vulnerable were more likely to receive the AstraZeneca vaccine. There is therefore potential for residual confounding in comparative analyses examining outcomes following receipt of specific vaccine types.

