Appendix Table 2: ICD-10 codes for identifying maternal venous thromboembolism

ICD-10	Condition
I26.0	Pulmonary embolism with mention of acute cor pulmonale
I26.9	Pulmonary embolism without mention of acute cor pulmonale
I80.1	Phlebitis and thrombophlebitis of femoral vein
I80.2	Phlebitis and thrombophlebitis of other deep vessels of lower extremities
I80.3	Phlebitis and thrombophlebitis of lower extremities, unspecified
O08.2	Embolism following abortion and ectopic and molar pregnancy
O22.3	Deep thrombophlebitis in pregnancy
O87.1	Deep phlebothrombosis in the puerperium
O88.2	Obstetric blood-clot embolism
I80.8	Phlebitis and thrombophlebitis of other sites
I80.9	Phlebitis and thrombophlebitis of unspecified site
I81	Portal vein thrombosis
I82.0	Budd Chiari syndrome
I82.1	Thrombophlebitis migrans
I82.2	Embolism and thrombosis of vena cava
I82.3	Embolism and thrombosis of renal vein
I82.8	Embolism and thrombosis of other specified veins
I82.9	Embolism and thrombosis of unspecified vein
O22.9	Venous complication in pregnancy, unspecified
O87.9	Venous complication in the puerperium, unspecified
G08	Intracranial and intraspinal phlebitis and thrombophlebitis
I63.6	Cerebral infarction due to cerebral venous thrombosis, nonpyogenic
I67.6	Nonpyogenic thrombosis of intracranial venous system
O22.5	Cerebral venous thrombosis in pregnancy
O87.3	Cerebral venous thrombosis in the puerperium
Considered but not included	
G95.1	Vascular myelopathies
H34.8	Other retinal vascular occlusions
I51.3	Intracardiac thrombosis, not elsewhere classified
I80.0	Phlebitis and thrombophlebitis of superficial vessels of lower extremities
K55.0	Acute vascular disorders of intestine
K64.5	Perianal venous thrombosis
K75.1	Phlebitis of portal vein
O22.2	Superficial thrombophlebitis in pregnancy
O22.8	Other venous complications in pregnancy
O69.5	Labour and delivery complicated by vascular lesion of cord
O87.0	Superficial thrombophlebitis in the puerperium
O87.8	Other venous complications in the puerperium
T80.1	Vascular complications following infusion, transfusion and therapeutic injection

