Appendix Table 3: ICD-10 codes for identifying hypertensive disorders of pregnancy

ICD-10	Condition
O11	Pre-eclampsia superimposed on chronic hypertension
O13	Gestational [pregnancy-induced] hypertension
O14.0	Mild to moderate pre-eclampsia
O14.1	Severe pre-eclampsia
O14.2	HELLP syndrome
O14.9	Pre-eclampsia, unspecified
O15.0	Eclampsia in pregnancy
O15.1	Eclampsia in labour
O15.2	Eclampsia in the puerperium
O15.9	Eclampsia, unspecified as to time period
Considered but not included for this category	
O10	Pre-existing hypertension complicating pregnancy, childbirth and the puerperium
O12	Gestational [pregnancy-induced] oedema and proteinuria without hypertension
O16	Unspecified maternal hypertension

SMR01 and SMR02 records with a relevant date of admission and any relevant ICD10 code recorded against main condition or any other condition will be used to identify admissions for the above 3 conditions. All SMR02 record types will be included (i.e. antenatal, delivery, and postpartum admissions).

Appendix 2: Rationale for selection of pregnancy-related outcome measures to be used in COPS study to assess impact of COVID-19 infection and safety of COVID-19 vaccination

A list of outcomes to be examined post-infection was drawn up in May 2020 for the initial COPS protocol document, based on what was known about COVID-19 at that point. A provisional list of outcomes to be examined post-vaccination (as part of vaccine safety monitoring) was drawn up in April 2021, based on a review of the following sources conducted up to 12 Feb 2021.

- MHRA public assessment record for the Pfizer vaccine (released at the time the MHRA first gave approval for use on 2 Dec 2020) - <https://www.gov.uk/government/publications/regulatory-approval-of-pfizer-biontech-vaccine-for-covid-19>
- MHRA public assessment record for the Oxford vaccine (released at the time the MHRA first gave approval for use on 30 Dec 2020) - <https://www.gov.uk/government/publications/regulatory-approval-of-covid-19-vaccine-astrazeneca>. No public assessment records for other vaccine types available at the time of review
- Data from the MHRA on possible adverse events reported through the Yellow Card scheme up to 31 Jan 2021. <https://www.gov.uk/government/publications/coronavirus-covid-19-vaccine-adverse-reactions>

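### The clean window for venous thromboembolism looks back only within the current pregnancy, so a clot from before pregnancy that is coded again can be counted as a new post-vaccination event

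*Protocol*

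**What the plan says.** Section 3.5.1 of the protocol applies clean windows "so that only new or incident cases occurring post vaccination will be counted". It then states that "a clean window of the current pregnancy will be applied for the venous thromboembolism" outcome, and for pregnancy-related bleeding and hypertensive disorders, and explains that "women will only be included if there is no prior record of these outcomes in the current pregnancy". Table 2 repeats the rule for venous thromboembolism ("No prior record in this pregnancy"). There it is a primary outcome with vaccination at any time, a risk period to the end of the postpartum period, and a background risk of 0.15%.

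The notes to Table 2 define vaccination at any time: "women vaccinated at any point from six weeks preconception to date of end of pregnancy (E) will potentially be included". Section 3.6 makes the vaccination date the index date, and section 3.2 follows pregnancies from conception.

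Appendix Table 2 lists obstetric codes alongside general ones (I26, I80 to I82, G08, I63.6, I67.6). One example is I80.2, "Phlebitis and thrombophlebitis of other deep vessels of lower extremities". The note after Appendix Table 3 says that events are found from "any relevant ICD10 code recorded against main condition or any other condition" on SMR01 and SMR02 records. No look-back well before the pregnancy, and no exclusion for earlier thromboembolism, is stated.

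**The concern.** The rule falls short of its stated purpose for this outcome. Hypertensive disorders are defined by pregnancy codes and, per Table 2, are diagnosable only after 20 weeks, so a window limited to the pregnancy suits them. Nearly all the bleeding codes are obstetric too. A deep vein thrombosis or pulmonary embolism can happen at any time in a woman's life, and its general codes do not say whether the event belongs to this pregnancy.

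Take a woman with a clot two months before conception, vaccinated around conception, whose clot is coded as a secondary diagnosis at an antenatal admission. She has no earlier record in this pregnancy, so she passes the filter and is counted as an incident post-vaccination event.

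The outcome is rare: 0.0015 × 5,000 = 7.5 expected events among vaccinated women at the first planned size in section 3.7, and 15 among 10,000. A few prevalent cases would be a visible share of the total, and in a safety study dilution towards no effect is the unwelcome direction.

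**Working it through.** The protocol gives no figure for the clean window, so there is none to reproduce. The check has three steps.

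**1. Length of the look-back.** Let d be the day of vaccination relative to conception. If the current pregnancy starts at conception (section 3.2), the look-back is max(0, d) days. If it is taken to include the six preconception weeks, the look-back is d + 42 days.

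| Vaccination day d | From conception | From six weeks before |
|---|---|---|
| −42 | 0 | 0 |
| −21 | 0 | 21 |
| 0 | 0 | 42 |
| 14 | 14 | 56 |
| 70 | 70 | 112 |

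For women vaccinated before conception the look-back is zero on the first reading and 0 to 6 weeks on the second. On neither reading does it reach more than six weeks behind conception, whenever the woman was vaccinated.

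**2. Equal re-coding in both groups.** Inputs: background risk p = 0.15% (Table 2); q = share of all women whose old clot is re-coded after the index date with no earlier record in this pregnancy. The documents do not give q, so a range is assumed. Observed risk ratio = (p × RR + q) / (p + q). For a true RR of 2.0:

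- q = 0.01%: 0.31 / 0.16 = 1.94
- q = 0.05%: 0.35 / 0.20 = 1.75
- q = 0.10%: 0.40 / 0.25 = 1.60

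The share of control events that are false is q / (p + q): 6%, 25% and 40%. Power for a true RR of 2.0 with 5,000 vaccinated women and 15,000 controls (unmatched comparison of two proportions, two-sided 5%) is 55.5% with no contamination, and 53.7%, 47.5% and 41.4% at these values of q. With a true RR of 1.0, equal re-coding leaves the ratio at 1.0.

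**3. Unequal re-coding.** If q is twice as high in vaccinated women, a true RR of 1.0 appears as follows:

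- q = 0.01% in controls: 0.17 / 0.16 = 1.06
- q = 0.05%: 0.25 / 0.20 = 1.25
- q = 0.10%: 0.35 / 0.25 = 1.40

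The doubling is also assumed. In the middle case the expected counts are 12.5 of 5,000 against 30 of 15,000. An approximate unmatched 95% interval is exp(ln 1.25 ± 1.96 × √(1/12.5 − 1/5,000 + 1/30 − 1/15,000)), which is 0.65 to 2.42.

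**The case against.** The strongest case against runs as follows.

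- **The start of the window is not stated.** That it begins at conception is inferred from section 3.2. Elsewhere the protocol treats the six preconception weeks as part of the exposure period. This stands, so a look-back of exactly zero for every preconception vaccinee cannot be asserted. It does not rescue the rule, because the wider reading adds at most six weeks.
- **There are safeguards.** Section 3.6 plans a sensitivity analysis without preconception vaccinees and their controls, and matches on gestational week, so controls have a similar look-back. Clinical vulnerability is a covariate (Table 4) in the adjusted model. These weaken the case for differential error. The sensitivity analysis keeps early-pregnancy vaccinees and does not alter the primary result. Prior thromboembolism is not itself a covariate.
- **The mechanism and rate are not documented.** The code list holds current-event codes only, so an old clot must be coded as if current. Nothing in the protocol shows how often that happens. Women vaccinated later also have a longer window, which catches some re-coding. All of this stands and limits what can be said about size.
- **Bleeding is not wholly immune.** D65 in Appendix Table 1 is a general code. True, but it is one code in an otherwise obstetric list.

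A reader might infer that the rule will create a false harm signal, since section 3.5.2 says that early in the programme "women who were clinically (extremely) vulnerable were more likely to receive the AstraZeneca vaccine". The documents do not support that. The sentence concerns which vaccine was received and says nothing about prior clots in vaccinated women overall. Upward bias would need an imbalance that remains after adjustment, and even the 1.25 above would sit well within chance. A reader might also tie the point to the thrombosis syndrome linked to one vaccine, but section 3.5.1 expressly separates this outcome from that condition.

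**Conclusion.** The point holds as a gap between a stated purpose and the rule meant to serve it. For venous thromboembolism the clean window cannot reliably separate incident from pre-existing clots, because it does not extend meaningfully before the pregnancy and the event definition accepts general codes in any position. This follows from the protocol's own rules and does not depend on where exactly the pregnancy is taken to start.

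The default consequence is dilution. Over assumed re-coding rates of 0.01% to 0.10%, a true risk ratio of 2.0 is seen as 1.94 to 1.60, so the effect is negligible at the low end and material at the high end. These figures assume equal re-coding in both groups, the Table 2 background risk, and one average rate across all gestations at vaccination.

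**What to change.** In section 3.5.1 and Table 2, for venous thromboembolism only, require no record of a listed code in a fixed look-back ending at the index date, as well as none earlier in the current pregnancy. Twelve months is an example; the length is a choice and should be stated with its reason. Apply it identically to vaccinated women and controls, using SMR01 and SMR02. State also where the current pregnancy starts for the clean-window rule.

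Restrict controls to those with the full look-back available. The study data begin on 01 January 2015. If 2014 records are not held, controls with an index date in the first 12 months would have to be dropped, about 12 of the 62 months of the pre-pandemic period. Keeping them with a shorter look-back would introduce an imbalance between the groups.

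The cost is one extra look-back in sources the protocol already uses. The downside is that a few women with a recent clot leave this one analysis, so it no longer covers recurrence in them.

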*Note that only women who have been followed-up to the end of the outcome-specific follow-up period at the end of each study period (i.e. 29 February 2020 for pre-pandemic controls and data of data extraction for pandemic controls) are eligible to be controls for a given outcome analysis.

3.7: Power calculation for matched cohort

It is estimated that by the end of 2021, full outcome and follow-up data will be available for approximately 5,000 vaccinated pregnant women, and by end of 2022, data available for 10,000 vaccinated pregnant women⁶.

Outcomes can be grouped as frequent (risk approximately 10%), moderate (approximately 3%), and rare (approximately 0.5%). Risk estimates for each adverse outcome are provided in Table 2. Based on these estimates and assumptions, with the relative risk of an event occurring post-vaccination set at 0.5, 1.2 and 2.0, and with statistical significance set at 0.05 and 0.01; power calculations for the various scenarios were calculated and are shown in Table 6. The power to detect a relative risk of 0.5, based on 5000 vaccinated pregnant woman against 15000 controls (ratio 1:3), when estimated

⁶ Personal communication with [name], July 2021.

adverse event occurrence is 0.5%, is 94%. This means that the study has a 94% chance of having a p-value of less than 5% (a statistically significant result and strong evidence against the null hypothesis) if there is really a difference in risk between vaccinated and unvaccinated women.

If the statistical power is low, the study sample size may be too small to detect any differences (i.e. under-powered) and therefore null results will need to be interpreted with caution. By convention, 80% is an acceptable level of power. It is acknowledged that the study may be under-powered to identify rarer outcomes.

Table 6: Power calculations scenarios

Cases	Controls	Estimated risk	Relative risk	Power %
5000	15000	0.50%	0.5	94
			1.2	10
			2.0	66
		3.00%	0.5	100
			1.2	45
			2.0	100
		10.00%	0.5	100
			1.2	94
			2.0	100
10000	30000	0.50%	0.5	100
			1.2	17
			2.0	94
		3.00%	0.5	100
			1.2	75
			2.0	100
		10.00%	0.5	100
			1.2	100
			2.0	100

4.0: Data Analyses

4.3: Descriptive analyses

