Appendix Table 1: ICD-10 codes for identifying pregnancy-related bleeding

ICD-10	Condition
	Obstetric haemorrhage
O44.1	Placenta praevia with haemorrhage
O45.0	Premature separation of placenta with coagulation defect
O45.8	Other premature separation of placenta
O45.9	Premature separation of placenta, unspecified
O46.0	Antepartum haemorrhage with coagulation defect
O46.8	Other antepartum haemorrhage
O46.9	Antepartum haemorrhage, unspecified
O67.0	Intrapartum haemorrhage with coagulation defect
O67.8	Other intrapartum haemorrhage
O67.9	Intrapartum haemorrhage, unspecified
O69.4	Labour and delivery complicated by haemorrhage from vasa praevia
O72.0	Third stage haemorrhage
O72.1	Other immediate postpartum haemorrhage
O72.2	Delayed and secondary postpartum haemorrhage
O72.3	Postpartum coagulation defects
O44.1	Placenta praevia with haemorrhage
	Early pregnancy bleeding
O03.1	Incomplete spontaneous abortion (miscarriage), complicated by haemorrhage
O03.6	Complete spontaneous abortion (miscarriage), complicated by haemorrhage
O04.1	Incomplete medical abortion (TOP), complicated by haemorrhage
O04.6	Complete medical abortion (TOP), complicated by haemorrhage
O05.1	Incomplete other abortion, complicated by haemorrhage
O05.6	Complete other abortion, complicated by haemorrhage
O06.1	Incomplete unspecified abortion, complicated by haemorrhage
O06.6	Complete unspecified abortion, complicated by haemorrhage
O07.1	Failed medical abortion, complicated by haemorrhage
O07.6	Other and unspecified failed medical abortion, complicated by haemorrhage
O08.1	Delayed or excessive haemorrhage following abortion and ectopic and molar pregnancy
O20.0	Threatened abortion
O20.8	Other haemorrhage in early pregnancy
O20.9	Haemorrhage in early pregnancy, unspecified
	Disseminated intravascular coagulation
D65	Disseminated intravascular coagulation
	Considered but not included
O43.2	Morbidly adherent placenta
O69.5	Labour and delivery complicated by vascular lesion of cord

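### Early pregnancy bleeding and DIC are examined only if a composite dominated by postpartum haemorrhage shows an association, so a signal in either component may be missed

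*Protocol*

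**What the plan says.** Section 3.5.1 treats pregnancy-related bleeding as one outcome. Its breakdown is descriptive and depends on the result for the broad outcome: "further descriptive analyses will be conducted looking at more specific diagnoses within these broader outcome groups if we find evidence for an association". The example given for bleeding is that "we can further disaggregate into early pregnancy bleeding, obstetric haemorrhage, and DIC".

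Table 2 lists pregnancy-related bleeding as a single primary outcome with no secondary outcome beneath it. Vaccination at any time is included, and follow-up runs to the end of the postpartum period. The background risk shown is "30.0 (for postpartum haemorrhage"); no rate is given for the whole composite or for any other part of it. Miscarriage, by contrast, has first- and second-trimester secondary outcomes, although their background risks are entered as unknown.

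Appendix Table 1 already splits the code list into obstetric haemorrhage, "Early pregnancy bleeding" and "Disseminated intravascular coagulation".

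One clean window covers the whole composite: "women will only be included if there is no prior record of these outcomes in the current pregnancy".

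Section 3.7 plans on "5000 vaccinated pregnant woman against 15000 controls (ratio 1:3") and later expects "data available for 10,000 vaccinated pregnant women". Section 4.4 adds a correction for multiple testing.

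**The concern.** A binary composite with a common component responds weakly to a change in a rare one. About 30% of women are expected to count as events through postpartum haemorrhage, so a doubling of a component that affects 1% of women raises the composite by a percentage point or less. If that does not amount to evidence of an association, the protocol plans no look at the component.

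Two features add to the dilution. Vaccination at any time qualifies, so women vaccinated after early pregnancy are in the comparison although they cannot have an early bleed after vaccination. The multiplicity correction also makes a positive composite harder to reach.

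At stake is the meaning of a null result. The study could report no association for pregnancy-related bleeding while its own linked data held a sizeable difference in early bleeding or DIC that nobody had tabulated.

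**Working it through.** **Inputs from the protocol.** 5,000 v 15,000 (section 3.7) and 10,000 v 30,000 (Table 6); 30% for postpartum haemorrhage (Table 2); a relative risk (RR) of 2.0 as one of the planning scenarios (section 3.7); significance level 0.05, taken as two-sided because sidedness is not stated.

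**Assumptions.** Early bleeding 0.5% to 5% of included women, and DIC 0.1%, because the protocol gives neither rate. All bleeding other than the component is set at 30%.

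**Formula.** Unmatched comparison of two proportions, p1 (vaccinated) and p0 (controls):

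power = Φ[(|p1 − p0| − 1.96·se0)/se1]

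Here se0 is the standard error with pooled variance and se1 the standard error with separate variances. This approximates the planned conditional logistic regression and leaves out the multiplicity correction.

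**The plan's own figure.** Section 3.7 states 94% power for a relative risk of 0.5 at 0.5% risk. With vaccinated risk = 0.5% × 0.5 the formula gives 66.5%. With vaccinated risk = 0.5%/0.5 = 1.0% it gives 94.8%. With the relative risk inverted in this way, all 18 cells of Table 6 reproduce within one point. The formula therefore matches the one used, and the relative-risk labels in Table 6 appear to run the wrong way round. That is a separate matter. Below, RR 2 means that the vaccinated risk is twice the control risk.

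**Composite risk.** For component rate e in controls and relative risk R:

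- Independent of other bleeding: p0 = 0.30 + 0.70e; p1 = 0.30 + 0.70·R·e.
- Never overlapping with other bleeding (upper bound on power): p0 = 0.30 + e; p1 = 0.30 + R·e.

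**Worked case: e = 1%, R = 2, independent, 5,000 v 15,000.** p0 = 0.3070 and p1 = 0.3140, a composite RR of 1.02. Pooled risk = 0.30875, se0 = 0.00754, se1 = 0.00757. Power = Φ[(0.0070 − 1.96 × 0.00754)/0.00757] = Φ(−1.03) = 15%.

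**Doubling of early bleeding** (power in %; composite shown as independent / non-overlapping)

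| Rate in controls | Composite, 5,000 v 15,000 | Direct, 5,000 v 15,000 | Composite, 10,000 v 30,000 |
|---|---|---|---|
| 0.5% | 6.8 / 9.8 | 94.8 | 9.7 / 15.4 |
| 1% | 15.2 / 26.2 | 99.9 | 25.9 / 46.4 |
| 2% | 45.3 / 74.2 | 100 | 73.9 / 95.8 |
| 3% | 78.1 / 97.2 | 100 | 97.2 / 100 |
| 5% | 99.4 / 100 | 100 | 100 / 100 |

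The rate at which a doubling reaches 80% power in the composite is about 2.2% (non-overlapping) to 3.1% (independent) with 5,000 vaccinated, and about 1.5% to 2.2% with 10,000.

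**Late vaccination.** If only a share f of vaccinated women can still have an early bleed after vaccination, the component rate in the composite falls to f·e. Take f = 0.3 (an assumption), 5,000 vaccinated and a doubling. Composite power is then 13-22% at e = 3%, 28-50% at 5% and 78-97% at 10%. A direct test confined to those 1,500 v 4,500 women has 81.5% power at 1%, 97.7% at 2% and 99.8% at 3%.

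**DIC at 0.1%, 5,000 v 15,000.**

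- Fivefold rise: composite risk 0.3007 to 0.3035 (independent) or 0.3010 to 0.3050 (non-overlapping); power 5.7% or 7.7%, against 99.4% directly.
- Doubling: power 3.1% or 3.4% in the composite, and 42.4% directly.
- DIC that accompanies a recorded haemorrhage adds nothing to the composite, so greater overlap lowers the composite figures further.

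**The case against.** The strongest reply is that the protocol gives no early-bleeding rate, so the loss cannot be shown to occur. This stands. A reader might infer that a large early-bleeding signal would be missed. The documents do not support that: at about 3% or more of all included women, a doubling would probably show in the composite. At 10,000 vaccinated it probably shows from about 2%. Some early-bleeding codes describe miscarriage, termination or ectopic pregnancy, and those women mostly cannot go on to postpartum haemorrhage. For them the higher, non-overlapping figures are the closer ones.

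A reader might also infer that separate analysis would rescue any DIC signal. It would not: a doubling at 0.1% has 42% power even when tested alone, and sections 3.7 and 5.0 already concede weak power for rare outcomes.

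Nor does Appendix 2 say that the bleeding outcome was kept because of evidence on haemorrhage after vaccination. It lists that evidence among many inputs, and section 3.5.1 separates the DIC in this outcome from the vaccine-associated thrombotic condition.

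The shared clean window means that an early bleed before vaccination also removes a woman from the later haemorrhage comparison. Excluding earlier events is a deliberate rule for incident cases, however, and its effect cannot be sized from the protocol.

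There are safeguards. Miscarriage is analysed separately, and section 4.3 plans plots of time from vaccination to outcome. These help only in part. The miscarriage outcomes do not capture bleeding in pregnancies that continue (codes O20.0, O20.8, O20.9). The section 4.3 summaries are organised by outcome, and the bleeding components are not outcomes.

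Finally, section 3.5.1 sets no threshold for evidence and does not forbid other tabulations, and an analysis plan not shown here might add them. The protocol nevertheless states the condition, and plans no other look at these components.

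**Conclusion.** The point holds as a risk of a missed signal. For early bleeding it applies when post-vaccination events affect fewer than about 2-3% of all included women with 5,000 vaccinated, or fewer than about 1.5-2.2% with 10,000. Below those rates a doubling often fails to move the composite, although a direct test would have about 95% power or more at 5,000 v 15,000 from a rate of 0.5% upwards. If many women are vaccinated after early pregnancy, the early-bleeding rate among those still at risk has to be higher before the composite responds. For DIC, the composite is close to blind to a fivefold rise at 0.1%, which a direct test would very probably detect; a doubling is out of reach either way.

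These figures rest on assumed component rates, a 30% rate for all other bleeding, an unmatched approximation and no multiplicity correction. The correction would lower composite power further. The protocol gives no rate that would place the study on the safe side.

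**What to change.** In Table 2, add early pregnancy bleeding and DIC as secondary outcomes under pregnancy-related bleeding, using the code groups already in Appendix Table 1. In section 3.5.1, remove the condition for these two, so that they are analysed and reported whatever the composite shows. DIC can be reported descriptively if events are too few to model.

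For early bleeding, restrict exposure to vaccination within an early-pregnancy window whose end the sponsor must define, and apply a clean window specific to that component. The sponsor should also decide whether the codes for haemorrhage after termination belong in it, since section 4.4 says that termination is not an outcome of interest. A separate obstetric haemorrhage outcome would add little, because it largely coincides with the composite.

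The cost is a few extra models and a few more tests in the multiplicity family. No new data or code lists are needed.
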